Caregivers (Intervention): The intervention will be delivered in six individual hour-long sessions during three months by a trained and certified masters-level, mental health professional Program Coach, using the VAMC Memphis Caregiver Center’s national certifying procedures. These include didactic, knowledge test, and supervised role play of intervention components. The first consent and assessment visit will also be in the facility during a patient clinic visit; consent can be obtained by the Research Associate or Program Coach. At this visit, the Program Coach will also begin the Intervention process to establish rapport; subsequent caregiver REACH sessions, approximately every two weeks, will be in the facility, by telephone, or by telehealth, dependent on patient appointments and caregiver desire. All sessions will be taped and treatment fidelity will assess intervention delivery, receipt, and enactment.

STUDY FLOW CHART

First Visit Sequence

Data Collection. A trained masters-level Research Associate will collect data from Caregiver and Veteran by telephone or at clinic visits (which typically occur every three months) at baseline (first assessment and consent visit), end of intervention (3 months), and 6 months.

REACH VA MS STATEMENT OF WORK (SOW)

Task 1: Develop Manual of Operations (MOP)

Month 1

Activities

- Finalize REACH VA MS sessions format
- Finalize REACH VA MS materials
- Finalize screening materials
- Finalize data collection protocol/battery
- Develop and print brochures and posters

Products

- Program Coach notebook, topics and scripts
- Caregiver Notebook
- Screening forms and scripts
- Data collection forms, scripts and documentation
- Brochures and posters

Task 2: IRB approval

Month 1

Activities

- Develop all IRB documents

Products

- IRB study approval

Task 3: Train personnel

Month 1

Activities

- Train Program Coach and research associate

Products

- Trained and certified staff

Task 4: Recruitment and Randomization

Months 1-15

Activities

- Mail brochures

- Telephone and screen potential participants

Products

- Approximately 46 Caregivers/Veterans screened
- 25 pairs recruited

Task 5: Intervention

Months 1-20

Activities

- Schedule and provide intervention for Caregivers

Products

- Intervention sessions provided

Task 6: Data Collection/Data Entry/Cleaning

Months 1-24

Activities

- Collect Caregiver data at baseline, 3 and 6 months
- Collect Veteran data at baseline, 3, and 6 months

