With loss of mobility in multiple sclerosis (MS) comes an increase in amount and types of caregiver assistance, with a concomitant increase in burden for the caregiver (1). In fact, effect on caregiver burden can be seen as a potential indicator of the efficacy of MS management (1), suggesting that the caregiver is an appropriate and independent target for MS therapeutic strategies (2).

MS patients report difficulty implementing and continuing with home exercise, mobility, and walking programs. This feasibility study will test integration of a successful behavioral caregiving intervention into clinical practice to improve functioning of Veterans with multiple sclerosis (MS) and their Caregivers. Caregivers of Veterans with MS will receive a behavioral caregiver intervention designed to address caregiver coping and management of patient concerns, with special focus on patient mobility and walking. A pre-post intervention design will compare outcomes for Veterans and Caregivers.

For Veterans, the intervention will target Caregiver participation in home-based Veteran mobility activities. Outcomes for Veterans will include the timed up and go test (TUGT), Expanded Disability Status Scale (EDSS), self-efficacy, fatigue, and depression. MS Caregivers report high burden, stress, and depression involved in caring for their loved ones, especially as mobility declines (3-5) and these outcomes are related to physical and emotional health status of the patient (2). For Caregivers, the intervention will focus on improving Caregiver coping and on managing MS-related problems. Outcomes for Caregivers will include depression, burden, anxiety, and number of Veteran MS problems and safety alerts reported, measured at baseline, End of Intervention (3 months), and 6 months.

RESEARCH QUESTIONS

Study Objectives include:

[figure not shown]
- 1) Test whether a caregiver intervention can be integrated into an MS clinical setting.
- 2) Determine whether Caregiver outcomes are improved.
- 3) Determine whether Veteran outcomes are improved.
- 4) Determine which types of Caregivers will benefit most.
- 5) Determine which types of Veterans will benefit most.
- 6) Refine materials for future clinical research, translation and implementation.

Hypotheses are related to both Veteran and Caregiver:

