 End of Intervention (3 months) and 6 month interview completed outside of -14/+14 day window
 Caregiver does not complete all 6 sessions within 4 1/2 months

RECRUITMENT

Caregivers will be recruited from the MS clinic and inpatient unit as Veterans are admitted or seen. We are requesting a waiver of informed consent and HIPAA authorization for recruitment purposes only, as a method of recruiting Veterans who have been diagnosed with MS, prior to participation in the study. Privacy risks to research subjects will be minimal. We will mail brochures to eligible Veterans. Veterans and/or Caregivers may contact us if they are interested in participating. If we do not hear from the Veteran and/or Caregiver in a reasonable amount of time after mailing the brochures, we will telephone the Veteran to give him/her more information about the study. The MS Clinic meets one day a week and study staff will be present to provide information and to screen Caregivers and Veterans. However, Veterans with MS are only seen in the MS clinic every three to six months, thereby potentially missing the enrollment period. Brochures will be mailed to all eligible participants. Brochures will also be strategically positioned around the hospital as well as in the MS clinic. Clinicians in the MS clinic will aid in the identification of eligible Veterans. Full informed consent and HIPAA authorization will be collected after screening as part of study enrollment. Our consent process for Caregivers and Veterans is overseen by the VAMC Memphis IRB and Research and Development Committee.

Screening. Participants must give permission to the Research Associate to be screened after hearing a study description that includes information about the research study and the screening process itself. Research study information includes a statement of the research (purpose, procedures), reasonably expected benefits to subjects or others, and costs. Screening process information includes duration of screening, alternatives, extent of confidentiality, and authorization for release of protected health information for research purposes.

Caregiver Consent and Veteran Consent. After screening, consent forms are provided to the Caregiver and Veteran participant. All participants must give written informed consent before becoming study participants and both Caregiver and Veteran must agree for the Caregiver to participate.

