Program Evaluation. Qualitative process evaluation data will focus on content and process issues of satisfaction, benefit, utility, changes, and support to determine if the intervention process or content needs modification for use in this setting. Data will be collected from Caregivers, Veterans, and clinicians. Clinicians will help determine whether the intervention was disruptive or supportive to patient care and the clinic process and any changes needed to facilitate integration.

Data Analysis

The primary outcomes are measured for all participants at baseline, three, and six months. Data analysis will use repeated measures analysis of variance (ANOVA) to compare baseline and post-intervention follow-up (3 month and 6 month) scores. Each outcome measure will be treated as independent of the others. For continuous variables, an effect size (d) of at least 0.2 SD improvement will be considered clinically significant. Effect sizes are estimated as mean change relative to estimated population standard deviation (44). With 50 subjects and 15% attrition, we will have 80% power to reject a false null hypothesis at $\alpha = 0.05$ when effect sizes fall between 0.3 and 0.4 for depression and anxiety outcomes, and when burden outcome is 0.3, as shown below in Table 2. Cohen considered effects of this magnitude to be between small to medium (44). Recruitment of more than 50 subjects or attrition less than 15% would yield greater power than 80% or allow for detection of smaller effect sizes as statistically significant. As previously mentioned, the means, standard deviations, and effect size values below are similar to those shown in Preliminary Results.

Table 2. Caregiver Baseline Data Values Observed from Previous Studies (7, 45):

Outcome Variable	Baseline (M \pm SD)	Reliability (r)	Power	Cohen's d	n
Depression (PHQ-9) (0-27)	7.80 \pm 5.94	0.84	0.80	.3	66
				.4	38
Anxiety (GAD-7) (0-21)	8.94 \pm 5.70	0.83	0.80	.3	71
				.4	40
Burden (Zarit 12) (0-48)	17.56 \pm 9.74	0.88	0.80	.3	50
				.4	29

Note: Estimates of sample size (n) include 15% attrition of subjects during study.

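### The power paragraph and Table 2 give n for caregiver scales at about twice the number of caregivers a single-group design needs, and the 80% claim depends on an undefined r being the pre-post correlation

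*Combined protocol and SAP*

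**What the plan says.** The power paragraph in Data Analysis states: "With 50 subjects and 15% attrition, we will have 80% power to reject a false null hypothesis" at alpha 0.05, for effects between 0.3 and 0.4 in depression and anxiety and 0.3 in burden. It adds: "Recruitment of more than 50 subjects or attrition less than 15% would yield greater power than 80" per cent. It refers to Table 2, whose title describes caregiver baseline data from previous studies. Table 2 gives, for 80% power and including 15% attrition, n at d = 0.3 / 0.4 of 66/38 (PHQ-9), 71/40 (GAD-7) and 50/29 (Zarit). A column headed Reliability (r) holds .84, .83 and .88 and is not explained.

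The same section says "Each outcome measure will be treated as independent of the others", and defines d as mean change over the population SD. Goals of Intervention gives the design: "A pre-post intervention design will compare outcomes for Veterans and Caregivers". There is no control group. Statement of Work, Task 4, plans "25 pairs recruited". Under Caregiver Consent and Veteran Consent, both members are participants: "both Caregiver and Veteran must agree for the Caregiver to participate".

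**The concern.** The word subjects is not defined. Every row of Table 2 is a caregiver scale under a caregiver title, and each outcome is analysed on its own, so the n that matters is the number of caregivers. That number is 25, which is below every n in the table and half of the 50 in the power sentence. A Veteran supplies no Zarit, GAD-7 or caregiver PHQ-9 score and cannot count towards n for them.

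Because d is scaled by the population SD, the SD of change depends on the correlation between baseline and follow-up. Table 2 has an r but calls it reliability, a term that can also mean internal consistency or short-interval test-retest agreement. Neither of these is the correlation across three or six months of an intervention meant to change the score.

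This is the only sample-size justification in the available text, and Hypothesis 2 predicts significant improvement in these outcomes. A reader judging a null result needs to know what about 21 caregivers could have shown, and on what assumption.

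**Working it through.** **Inputs.** From Data Analysis and Table 2: alpha 0.05 (sidedness not stated; two-sided reproduces the table), power 0.80, d = 0.3 and 0.4, r = .84/.83/.88, attrition 15%. From the Statement of Work: 25 pairs. Completers: 25 × 0.85 = 21.25, about 21. K = (1.960 + 0.842)² = 7.849.

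**Step 1: reproduce Table 2.** Take r as the pre-post correlation, so the variance of change in SD units is 2(1−r). A single-group paired comparison needs 2(1−r)K/d² completers. Two calculations give all six printed values exactly:

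- A, two-group formula, n per group: 4(1−r)K/d², rounded up, divided by 0.85, rounded up.
- B, single-group formula counting both pair members: 2 × [2(1−r)K/d² rounded up], divided by 0.85, rounded up.

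| Scale, d | 2(1−r)K/d² | 4(1−r)K/d² | A | B | Table 2 | Caregivers only |
|---|---|---|---|---|---|---|
| PHQ-9, 0.3 | 27.9 | 55.8 | 66 | 66 | 66 | 33 |
| PHQ-9, 0.4 | 15.7 | 31.4 | 38 | 38 | 38 | 19 |
| GAD-7, 0.3 | 29.7 | 59.3 | 71 | 71 | 71 | 36 |
| GAD-7, 0.4 | 16.7 | 33.4 | 40 | 40 | 40 | 20 |
| Zarit, 0.3 | 20.9 | 41.9 | 50 | 50 | 50 | 25 |
| Zarit, 0.4 | 11.8 | 23.5 | 29 | 29 | 29 | 15 |

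The last column is the single-group completers, rounded up, divided by 0.85 and rounded up. For the first cell (66), other formulas fail: one-sided gives 52, variance 1−r² about 61, and r ignored about 103. So r was used as a pre-post correlation, and each printed n is about twice the caregiver count.

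**Step 2: what 21 caregivers can detect at the plan's r.**

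- Three-visit repeated measures ANOVA (the planned method), assuming compound symmetry and the same d at 3 and 6 months: noncentrality λ = n(2/3)d²/(1−r), df 2 and 40. For burden at d = 0.3, λ = 21 × (2/3) × 0.09 / 0.12 = 10.5, power 80%.
- Two-visit paired t: dz = d/√(2(1−r)), noncentrality dz√21, df 20. For burden at d = 0.3, dz = 0.3/√0.24 = 0.612, noncentrality 2.81, power 76%.

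| | r | Detectable d, ANOVA | Detectable d, paired t | Power at d = 0.3, ANOVA / t | Power at d = 0.4, ANOVA / t |
|---|---|---|---|---|---|
| Depression | .84 | 0.345 | 0.364 | 67% / 64% | 91% / 87% |
| Anxiety | .83 | 0.355 | 0.375 | 65% / 61% | 89% / 85% |
| Burden | .88 | 0.298 | 0.315 | 80% / 76% | 97% / 94% |

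**Step 3: dependence on r.** The r below 0.83 are assumptions, since the documents give no other pre-post correlation. n = 21 throughout.

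| r | Power at d = 0.3, ANOVA / t | Detectable d, ANOVA | Detectable d, paired t |
|---|---|---|---|
| 0.5 | 26% / 26% | 0.61 | 0.64 |
| 0.6 | 31% / 31% | 0.55 | 0.57 |
| 0.7 | 41% / 39% | 0.47 | 0.50 |
| 0.8 | 57% / 54% | 0.39 | 0.41 |
| 0.88 | 80% / 76% | 0.30 | 0.31 |

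Eighty per cent power at d = 0.3 needs r of about 0.88 by ANOVA or 0.89 by paired t; at d = 0.4 it needs 0.78 or 0.81.

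**The case against.** The best defence is that 50 subjects means 25 pairs. Both members consent as participants, and counting both reproduces Table 2 exactly. On the plan's own r, the planned ANOVA with 21 caregivers then detects effects inside the stated 0.3 to 0.4 range for depression and anxiety, and about 0.3 for burden. The 76% for burden comes from a two-visit t-test that the plan does not name. All of this stands, and it rules out the tempting inference that having 25 caregivers instead of 50 destroys the power. The doubled n and the doubled count offset each other. The defence does not make 50, or any n in Table 2, the number of people who supply a caregiver score.

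On r, a reader might infer that Cronbach's alpha was used by mistake, because Caregiver Outcomes and Veteran Outcomes quote alphas of similar size (Zarit 0.85, PHQ-9 .86). The documents do not show this. The Table 2 values differ from those alphas in opposite directions, no alpha is given for the GAD-7, and the table's title attributes its values to previous studies, which may report r in some form. A reader might also take Table 1 as evidence that the true correlation is far lower. It cannot carry that: the type of test behind its p-values is not stated, the means and SDs are rounded, and the scales were shortened versions. What stands is that r is undefined and the result depends on it.

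**Conclusion.** The stated sample sizes are wrong in unit for the outcomes they support. Each caregiver score will come from 25 people (about 21 completers), and every Table 2 n is about double the single-group requirement. The documents do not show whether a two-group formula or a count of both pair members produced this.

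The 80% claim itself is nearly preserved at the plan's r: detectable d is 0.345/0.355/0.298 by ANOVA (compound symmetry, sustained effect) or 0.364/0.375/0.315 by paired t. It fails if the pre-post correlation is materially lower, falling to about 26% to 41% at d = 0.3 for r of 0.5 to 0.7. That range is an assumption, so this is a sensitivity the plan omits and not a demonstrated shortfall.

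The plan also says "an effect size (d) of at least 0.2 SD improvement will be considered clinically significant". A reader might infer that power is claimed at 0.2. It is not, so there is no contradiction, but a stated detectable d would make the gap visible. For a feasibility study this is worth correcting and does not call for redesign.

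**What to change.** First confirm that the unit is 25 pairs. Then:

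1. Rewrite the power sentence along these lines: *With 25 caregivers and 15% attrition (about 21 analysed), the study has 80% power to detect d of about 0.35 for depression, 0.36 for anxiety and 0.30 for burden, if the pre-post correlations are .84, .83 and .88.* In the later sentence, change 50 subjects to 25 caregivers.
2. Restate Table 2 in caregivers by one named single-group method. By normal approximation the enrolled n at d = 0.3 / 0.4 is 33/19 (depression), 36/20 (anxiety) and 25/15 (burden), which agrees with the sentence above: with 21 completers, √(2(1−r)K/21) gives 0.346, 0.356 and 0.300. State the method and that the test is two-sided.
3. Define r as the baseline-to-follow-up correlation used in the calculation, and say whether the cited studies report it as such.
4. Add one line of detectable d with 21 completers over a range of r, for example by ANOVA: 0.61 at .5, 0.55 at .6, 0.47 at .7, 0.39 at .8 and 0.30 at .88, with the compound-symmetry and sustained-effect assumptions stated.

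The cost is two reworded sentences, one defined column, one recomputed column and one added line. Design and recruitment do not change. The only downside is that the stated figures look less favourable at lower r.

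### The power sentence, as worded, offers 80% power for any depression or anxiety effect from 0.3 to 0.4 with 50 subjects, which Table 2 does not support at the lower end; the wording misleads, the table is sound

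*Combined protocol and SAP*

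**What the plan says.** The power statement is in the Data Analysis section of the combined protocol and SAP. It opens "With 50 subjects and 15% attrition, we will have 80% power to reject a false null hypothesis" at a 0.05 level, and then gives the conditions: "when effect sizes fall between 0.3 and 0.4 for depression and anxiety outcomes", "and when burden outcome is 0.3, as shown below in Table 2".

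Table 2, directly below, lists caregiver outcomes with a reliability r and the n for 80% power:

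| Outcome | r | n at d = 0.3 | n at d = 0.4 |
|---|---|---|---|
| Depression (PHQ-9) | 0.84 | 66 | 38 |
| Anxiety (GAD-7) | 0.83 | 71 | 40 |
| Burden (Zarit 12) | 0.88 | 50 | 29 |

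The note under the table reads "Estimates of sample size (n) include 15% attrition of subjects during study", so these n are to be compared with 50 directly. The section states neither the variance formula nor whether the test is one- or two-sided. Task 4 of the Statement of Work sets recruitment at 25 caregiver/Veteran pairs.

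**The concern.** The sentence makes 80% power conditional on the effect lying in an interval, and a reader will apply that at any point in it, including 0.3. The parallel burden clause invites this, because it is a correct statement of power at 0.3. For depression and anxiety, however, the cited table asks for 66 and 71 subjects at 0.3, and the plan has 50.

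The lower end of the interval matters. The section treats an improvement of 0.2 SD as clinically significant. It also calls its effect sizes similar to the preliminary results, where Table 1 (shorter scales, N = 125) shows 0.26 for depression and 0.35 for anxiety. A null result at a true effect of 0.3 would be read as carrying a 20% miss rate, when Table 2's own basis implies about 31-35%.

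**Working it through.** **Inputs.** From Data Analysis and Table 2: 50 subjects, 15% attrition, power 0.80, alpha 0.05, and r and d as tabulated. From the Statement of Work, Task 4: 25 pairs. Assumed, because not stated: a two-sided test and the variance factor found in step 1.

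**Step 1: reproduce Table 2.** The formula that works is

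completers = (1.96 + 0.84)² × 4(1 − r) / d², rounded up; enrolled = completers / 0.85, rounded up.

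The squared sum of z values is 7.849 before rounding.

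- Depression: 7.849 × 0.64 / 0.09 = 55.8 → 56; 56 / 0.85 = 65.9 → **66**. At 0.4: 31.4 → 32; 37.6 → **38**.
- Anxiety: 7.849 × 0.68 / 0.09 = 59.3 → 60; 70.6 → **71**. At 0.4: 33.4 → 34; 40.0 → **40**.
- Burden: 7.849 × 0.48 / 0.09 = 41.9 → 42; 49.4 → **50**. At 0.4: 23.5 → 24; 28.2 → **29**.

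All six cells match, so 66 and 71 are the plan's real figures. One-sided alpha and the factors 1, 1 − r, 1 − r², 2(1 − r) and 2(1 − r²) do not reproduce the whole table.

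**Step 2: detectable effect with 50 enrolled.** Completers = 50 × 0.85 = 42.5. Detectable d = 2.80 × √(4(1 − r) / 42.5):

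- Depression 0.344, anxiety 0.354, burden 0.298.
- With 42 completers: 0.346, 0.356 and 0.300.

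A check that needs no formula is to scale the printed n, since n varies as 1/d². Depression: 0.3 × √(66/50) = 0.345 and 0.4 × √(38/50) = 0.349. Anxiety: 0.3 × √(71/50) = 0.357 and 0.4 × √(40/50) = 0.358. Burden: 0.3 × √(50/50) = 0.300.

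**Step 3: power at d = 0.3.** Power = Φ(d × √(42.5 / (4(1 − r))) − 1.96):

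- Depression: Φ(0.3 × 8.149 − 1.96) = Φ(0.485) = 0.686 (0.681 with 42 completers).
- Anxiety: Φ(0.3 × 7.906 − 1.96) = Φ(0.412) = 0.660 (0.655 with 42).
- Burden: Φ(0.3 × 9.410 − 1.96) = Φ(0.863) = 0.806 (0.801 with 42).

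Read as a promise over the whole interval, the sentence falls short over its lower 44-49% for depression (0.30 to 0.344-0.349) and 54-58% for anxiety (0.30 to 0.354-0.358).

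**Step 4: dependence on the basis.** Table 2 concerns caregivers, and 25 pairs contain 25 caregivers (25 × 0.85 = 21.25 completers). The factor 4(1 − r) is the per-group formula for comparing change between two groups, whereas the design is single-group pre-post. With r taken as the pre-post correlation, the paired factor is 2(1 − r).

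| Basis | Detectable d: depression / anxiety | Power at 0.3: depression / anxiety |
|---|---|---|
| 50 enrolled, 4(1 − r), as Table 2 | 0.34-0.35 / 0.35-0.36 | 68-69% / 65-66% |
| 25 caregivers, 2(1 − r), paired t, 21 completers | 0.36 / 0.375 | 64% / 61% |
| 25 caregivers, 4(1 − r), normal approximation | 0.49 / 0.50 | 41% / 39% |
| 50 caregivers, 2(1 − r) | 0.24 / 0.25 (normal approximation) | 92% / 90-91% (paired t, 42-43 completers) |

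Under the normal approximation the first two bases coincide, because 2(1 − r) / 21.25 = 4(1 − r) / 42.5. The t distribution makes the second slightly worse.

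**The case against.** The best defence is that the sentence describes a bracket. At a fixed n, exactly 80% power occurs at one effect size per outcome, so the authors may mean that this effect lies between 0.3 and 0.4. Three things support that reading. Fifty lies between the tabulated n (38 < 50 < 66; 40 < 50 < 71). Burden, the one outcome whose n at 0.3 is exactly 50, gets a point instead of a range. The following sentence treats 80% at 50 subjects as a threshold, beyond which smaller effects become detectable. On this reading the sentence and the table agree.

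That defence stands as far as it goes. A reader might infer that Table 2 is miscalculated, or that the power claim is simply false. The documents support neither: all six n reproduce, and the bracket reading is plausible. What remains is that the words also state a condition for 80% power, that condition is wrong at 0.3, and the two effects the reader needs are not given.

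A second objection is that the size of the shortfall rests on an inferred formula and an unclear count. This also stands. With 50 caregivers and a paired factor the sentence would be true over its whole range; with 25 caregivers and Table 2's factor no effect in the range would reach 80%.

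A third is that little harm follows, since 66 and 71 are printed just below and this is a feasibility study. That limits the consequence, but the correction is one sentence.

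**Conclusion.** The power sentence is misleading and should be restated; Table 2 needs no arithmetic correction. On Table 2's own basis, 50 subjects with 15% attrition reach 80% power at about d = 0.34-0.35 for depression, 0.35-0.36 for anxiety and 0.30 for burden. Power at 0.3 is about 68-69% for depression and 65-66% for anxiety.

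These figures assume a two-sided test, the factor 4(1 − r), and that the 50 subjects are the unit Table 2 counts. If the unit is the 25 caregivers and the analysis is paired, with r as the pre-post correlation, the detectable effects are about 0.36 and 0.375 and power at 0.3 is about 64% and 61%. The documents do not settle which basis applies, so none of these values should be entered as final. It would also go too far to infer that recruitment must rise to 66 or 71: the point concerns what the sentence tells the reader.

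**What to change.** Replace the range with one detectable effect per outcome and the power at d = 0.3, and state the basis in the same sentence: number of caregivers enrolled and expected to complete, variance formula, meaning of r, and sidedness. On Table 2's present basis it could read:

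> Assuming 50 enrolled, 15% attrition, a two-sided 0.05 test and a change variance of 4(1 − r) in SD units, 80% power is reached at about d = 0.34-0.35 for depression, 0.35-0.36 for anxiety and 0.30 for burden; at d = 0.3 power is about 68-69% for depression and 65-66% for anxiety.

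Before adopting any figures, settle whether the 50 subjects are caregivers or both members of 25 pairs, and whether the factor suits a single-group pre-post comparison. Then recompute and keep the same form.

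The cost is one sentence, plus a recalculation if the basis changes. On Table 2's basis the stated power becomes somewhat less favourable. No more participants are needed, and the design does not change.

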Preliminary Studies. The research team brings decades of experience working with caregivers and MS patients and a track record of successfully implementing caregiving and MS interventions in the VHA system to help ensure success of the proposed project. The REACH VA intervention was designed and tested in VHA and is implemented by VHA clinicians daily to help Veteran Caregivers. The caregiving team of [name], [name], [name], and [name] have more than 20 years' experience in this intervention and in working with caregivers as Principal Investigators for REACH I and II ([name]) and REACH VA ([name] and [name]). [name] and [name]

are Co-Directors of VA’s national Caregiver Center, located at Memphis VA Medical Center, with responsibility for implementing REACH VA as a national clinical program. The Caregiver Center trains and certifies VA staff nationally to provide caregiver interventions. The REACH model is also being implemented into Tribal Organizations to serve Native American/Alaskan Native dementia caregivers, funded by the Rx Foundation ([name]).

Caregivers participating in the REACH II and REACH VA interventions show similar significant improvement in outcomes (6-8). Table 1 below shows data from the current REACH VA dementia program in the VA (8) that has a similar number of sessions as the proposed project but used shorter versions of the outcome measure scales. The analysis section has data from the 2007 to 2009 REACH VA pilot study that had 12 sessions and full versions of the scales (2).

Table 1. REACH VA Program Caregiver Outcomes (N = 125) (8)

Variable	Baseline M ± SD	Follow-up M ± SD	p -value	Cohen’s d
Burden (0-16)	7.7 ± 4.0	6.4 ± 3.5	<.001	.33
Depression (0-6)	2.0 ± 1.9	1.5 ± 1.7	.006	.26
Anxiety (0-6)	2.9 ± 2.1	2.2 ± 1.9	<.001	.35
Safety (0-9)	1.5 ± 1.1	1.1 ± 1.1	<.001	.36
Behaviors (0-25)	13.0 ± 3.7	11.8 ± 4.6	.001	.34
Behaviors bother (0-25)	8.0 ± 4.4	7.3 ± 5.3	.164	.16

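### Table 2's sample sizes use an unexplained reliability as the baseline-to-follow-up correlation and carry twice the one-group factor, so the 80% power statement cannot be verified

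*Combined protocol and SAP*

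**What the plan says.** The study has one group measured before and after the intervention. The Data Analysis section says: "Data analysis will use repeated measures analysis of variance (ANOVA) to compare baseline and post-intervention follow-up" scores at 3 and 6 months. It defines the effect size d as mean change divided by the population SD, not by the SD of the change.

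On power it says "With 50 subjects and 15% attrition, we will have 80% power to reject a false null hypothesis" at a 5% level "when effect sizes fall between 0.3 and 0.4 for depression and anxiety outcomes, and when burden outcome is 0.3". Table 2, captioned "Caregiver Baseline Data Values Observed from Previous Studies (7, 45", supports this. Its column headed "Reliability (r" reads 0.84 (PHQ-9), 0.83 (GAD-7) and 0.88 (Zarit 12). Its n at d = 0.3 / 0.4, including 15% attrition, are 66/38, 71/40 and 50/29. The section gives no formula, no sidedness and no definition of r.

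Task 4 of the Statement of Work plans 25 recruited pairs, so 25 caregivers.

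Preliminary Studies adds "Table 1. REACH VA Program Caregiver Outcomes (N = 125) (8", which gives means, SDs and p-values before and after the current dementia program. That program "used shorter versions of the outcome measure scales". The same section says that the analysis section draws on "data from the 2007 to 2009 REACH VA pilot study that had 12 sessions and full versions of the scales".

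**The concern.** Because d is scaled to the population SD, n cannot be computed without the correlation between baseline and follow-up: the SD of change is √(2(1-r)) population SDs. The only candidate in Table 2 is the reliability column. A reliability, whether internal consistency or short-interval retest, need not equal the correlation over 3 or 6 months in people who receive an intervention between the measurements. The two would be expected to differ if caregivers respond unequally or their situation changes.

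The multiplier on (1-r) also matters. If it is not the one for a single group measured twice, the tabulated n do not follow from this design even when r is right. At stake is whether the 80% figure, the plan's only statement of what the study can detect, can be relied on.

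**Working it through.** **Inputs.** From Data Analysis and Table 2: α = 0.05, power 0.80, 15% attrition, d = 0.3 and 0.4, r = 0.84, 0.83, 0.88. Two-sided testing is assumed. Completers: 50 × 0.85 = 42.5 (42 used); 25 × 0.85 = 21.25 (21 used).

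**Step 1: reproduce Table 2.** Take m = k(1-r)(1.96+0.84)²/d², round up, divide by 0.85 and round up again. For PHQ-9 at d = 0.3 with k = 4: 4 × 0.16 × 7.85/0.09 = 55.8, so 56; 56/0.85 = 65.9, so 66.

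| Outcome | r | Printed n (d = 0.3/0.4) | k = 4 | k = 2 |
|---|---|---|---|---|
| PHQ-9 | 0.84 | 66/38 | 66/38 | 33/19 |
| GAD-7 | 0.83 | 71/40 | 71/40 | 36/20 |
| Zarit 12 | 0.88 | 50/29 | 50/29 | 25/15 |

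With k = 4 all six match. With k = 2, the factor for a one-group paired comparison, none do. The k = 4 formula also recovers the power sentence: with 42.5 completers, the detectable d = 2.80 × √(4(1-r)/42.5) is 0.34 (depression), 0.35 (anxiety) and 0.30 (burden).

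**Step 2: what the doubling does.** If the printed n count caregivers, they suffice for a one-group test whenever 2(1-r') ≤ 4(1-r), that is r' ≥ 1 - 2(1-r): 0.68, 0.66 and 0.76. The doubling thus partly offsets a lower correlation. If the printed n count both members of a pair, that margin disappears.

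**Step 3: power as a function of r.** Paired t-test on one follow-up, noncentral t, SD of change √(2(1-r)). The r values below 0.83 are assumptions for sensitivity.

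| r | Power, 42 completers (d = 0.3/0.4) | Power, 21 completers (d = 0.3/0.4) | Detectable d at 80%, 42 / 21 |
|---|---|---|---|
| 0.40 | 41%/64% | 22%/36% | 0.49 / 0.70 |
| 0.56 | 53%/77% | 29%/46% | 0.42 / 0.60 |
| 0.70 | 69%/90% | 39%/62% | 0.34 / 0.50 |
| 0.83 | 90%/99% | 61%/85% | 0.26 / 0.38 |
| 0.84 | 92%/99% | 64%/87% | 0.25 / 0.36 |
| 0.88 | 97%/>99% | 76%/95% | 0.22 / 0.32 |

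The gap between 42 and 21 comes from the subject count, not from r.

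**Step 4: the planned three-time-point ANOVA.** Assume means 0, d, d and equal correlations; the F test has 2 and 2(n-1) degrees of freedom and noncentrality n(2d²/3)/(1-r). For 80% power, 42 completers need r of about 0.75 (d = 0.3) or 0.55 (d = 0.4). With 21, about 0.88 or 0.78 is needed.

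**Step 5: sensitivity check from Table 1 (N = 125).** If its p-values are from paired t-tests, SD of change = mean change × √125/t, and r = (SD₁² + SD₂² - SD of change²)/(2 SD₁ SD₂).

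- Depression: p = .006 gives t = 2.80; SD of change = 0.5 × 11.18/2.80 = 2.00; r = (3.61 + 2.89 - 4.00)/6.46 = 0.39. Rounding of the printed values allows 0.04 to 0.64.
- Behaviors: p = .001 gives r of about 0.56 (0.42 to 0.68).
- Behaviors bother: p = .164 gives r of about 0.35 (0.12 to 0.54).
- Anxiety and burden: p < .001 gives only lower bounds, about 0.33 and 0.34.

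**The case against.** The formula is inferred, and the factor of 4 has readings that suit a one-group design. Counting both members of 25 pairs gives 50 subjects, and doubling the one-group n before rounding is the same as 4(1-r). A three-time-point ANOVA with evenly spaced means (0, d/2, d) and the lower-bound sphericity correction has noncentrality nd²/(4(1-r)), again a factor of 4, although its exact F version gives n that are 2-3 above those printed. The plan states neither reading. A reader might infer that a two-arm formula was applied by mistake. It would fit the figures, but the documents do not establish it.

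A reader might also infer that the column is internal consistency. The Cronbach's alphas under Outcomes are 0.85 for the Zarit and .86 for the PHQ-9 (the latter under Veteran outcomes), against 0.88 and 0.84 in Table 2. The mismatch leaves a retest correlation possible. What stands is that the column is undefined.

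Table 1 might be read as disproving r = 0.84. It cannot: its scales are shorter, which would be expected to lower the correlation, its caregivers look after people with dementia, its test is not named, and for anxiety and burden it sets no upper limit.

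The strongest temptation is to call the trial underpowered. At the printed r it is not with 42 caregivers. With 21, the detectable d for depression and anxiety falls within the plan's range of 0.3 to 0.4. Finally, this is a feasibility study whose first objective is integration into clinic. That limits the weight of the point, but both hypotheses predict significant improvement and the 80% claim is explicit.

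**Conclusion.** The concern holds as a problem of verification that should be fixed. The tabulated n do not follow from a one-group paired comparison at the printed r: they are about twice what it needs, unless the doubling counts both members of a pair or reflects an unstated conservative correction. In the other direction, the correlation they rest on is not shown to be the 3- or 6-month one.

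The net effect depends on r. At 0.83 to 0.88 the power sentence holds with 42 caregiver completers. With 21, only burden at d = 0.3 narrowly misses: 76% by paired t, and about 80% by the ANOVA of Step 4, whose threshold is the printed 0.88. If r were near 0.4, the detectable d would be 0.49 with 42 completers and 0.70 with 21. The documents do not tell the reader which case applies.

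These conclusions assume two-sided testing, the inferred formula, and the means and equal correlations stated for the ANOVA. Table 1 is a sensitivity check only.

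**What to change.** 1. State what the r column is. Replace it with the observed baseline-to-follow-up correlation, or the SD of change, from the earlier REACH VA data, with its follow-up interval.
2. Recompute Table 2 for a one-group repeated-measures contrast, using one stated formula and the number of caregivers: 25 enrolled, about 21 completers.
3. Show the detectable d for r from about 0.4 to 0.88.
4. Restate the 80% power sentence from that table.

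The cost is one sourced number, one recalculation and a reworded sentence, with no change to study conduct. The downside is that the stated power may become less favourable if the observed correlation is below the printed one.
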